Families will be recruited from pediatric practices in our Practice-based Research Networks (PBRNs) in several ways. Each practice will have children who meet age, height, and weight criteria flagged in their charts, and we will use multiple approaches to recruit families. First, we will establish a ResearchMatch approach to recruiting in each PBRN. ResearchMatch, an online recruitment tool, will accrue families in one of two ways. At intake for a well- or sick-child visit, forms designed to acquaint families with the study will be introduced by PLAN coaches, and families can sign up for additional information about this study. Their information will be entered into a database by the PLAN coaches, and they will be contacted if they meet criteria. In addition, we will set up a website that they will be directed to in a flyer, and they can sign up to participate from the website. Since the pediatrician generally will not have information on parental health, this will need to be collected prior to deciding study eligibility, and the family database will assist in this endeavor by including information about all family members after a phone screen is conducted by the PLAN coaches with the participating parent. Second, PBRN practices post study advertisement at offices for interested families to visit the study website to complete questionnaires to ensure they meet eligibility criteria. If the families meet eligibility criteria, a PLAN coach will follow up with the families to schedule their first appointment at their earliest convenience. At this appointment, the PLAN coach will confirm the families' interest to participate and eligibility prior to participation. Third, Plan coaches will meet with families during well-child visits to introduce the study, assess their interest, and explain next steps. Each of these methods in collecting their information regarding interest and eligibility will be preceded by getting their verbal consent over the phone or a check box indicated on the web pages.

During recruitment, PLAN coaches will explain that there is a 50/50 possibility of getting one treatment over the other treatment. This will be like a flip of the coin and no one can just pick one treatment or the other. This study is testing if the FBT is as good as the care provided by their doctors normally given or better. Randomization will occur after the first appointment.

Inclusion Criteria

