Power computations for PLAN employ simulations and two-sided tests at the 0.05 level of significance. The simulations reflect the planned primary analysis of covariance and the fact that this is an individually randomized group treatment trial with the coach (N=3 per site) nested within the site (N=4 sites) in the FBT group but with no such nesting in the UC group. The analysis of covariance that is simulated in the power computations treats the 24-month value of the outcome measure as the dependent variable and the baseline value as a covariate. The use of this approach reflects the primary study goal of comparing 24-month values across groups, with the outcome being compared being percent over normalized BMI in the participating child. Each result is based on 1000 simulations.

Tabulated power values employ sample sizes of 528 and that are between 65% and 95% of that total. Effect size estimates are generated using considerations and preliminary data discussed below. Usual care data involving an intervention and subjects most similar to our UC group is provided by Kalarchian⁶¹ who randomized 81 8-12-year-old children with obesity to a usual care control condition and found an average percent overweight change of -0.17 ± 10.08 at 1 year. We expect some deterioration in this group at 2 years but will assume conservatively for the purpose of power computations that the two-year change will be 0 ± 10.08 in the UC group in the proposed research. Our estimated change in the FBT group begins with a review of seven studies^{20,62-67} authored by [name]. There were 314 overweight/obese children in those studies who received FBT interventions similar to the one we will employ. When we combined

the data for those 314 children, we found an overall average decrease in percent over BMI of 10.6 ± 15.3 at 24 months.

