Table 1 contains the results of the power computations using the parameters discussed above, assuming the compound symmetry covariance structure in both study arms and assuming an intraclass correlation coefficient (ICC) in the UC group of 0.01 and ICCs in the FBT group of 0.04, 0.06, 0.10, and 0.15. We assume a small ICC in the UC group of 0.01 because there is no clustering within that group meaning that the ICC should be essentially zero. While we do not have data with which to estimate the ICC in the FBT group, we note that many cluster trials that involve group interventions have reported ICCs in the 0.01 to 0.05 range. Since the PLAN intervention is individualized and since we expect PLAN children to have no contact with one another, we do not face the impact on the ICC that is present in many cluster trials. This argues for a very small ICC in the FBT group. By contrast, the fact that the same coach will be responsible for multiple children will inevitably increase the ICC above where it might otherwise be. Based on these considerations, we tabulate power for ICCs in the FBT group that range from 0.04 to 0.15. However, the many other studies that have used group interventions while yielding ICCs below 0.05 suggests that the ICC ultimately observed in PLAN will be substantially less than 0.1.

Results in Table 1 indicate that if we recruit 100% of our original target of 528 families, power will be excellent for all tabulated scenarios with an ICC in the FBT group of 0.1 or less. For an ICC

no bigger than 0.1, power remains adequate for most scenarios if we recruit at least 80% of the target (N = 432). If recruitment is below the 80% figure, an adequate power of at least 0.8 requires either the smaller of the two tabulated standard deviations or a mean difference that is at least 60% of the value observed in [name] studies (difference at least 6.4).

Table 1: Statistical power for two sided tests at the 0.05 level of significance.

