The DCC will use the REDCap randomization module to create an online password protected randomization system that will facilitate the random assignment of families. When the website is entered, the user will provide information that establishes the eligibility of the family. Group assignments will be revealed only if all eligibility criteria are satisfied. To avoid temporal bias, randomization will be blocked within clinic using random block sizes in order to preclude the possibility that investigators might know in advance the assignment of the last family in a particular block.

2. Standardization of Height and Weight Measurements

Verifications for collecting and entering the data for the height and weights will be followed to decrease bias. All stadiometers and scales used will be calibrated and consistent between all sites. PLAN coaches and assessors will be trained and tested on protocols for obtaining these measures. All weight measurements will be taken according to a uniform protocol and written on hard copy measurement sheets. The handwritten weights will be manually entered into the REDCap database by a blinded measurement coach, which will eliminate potential measurement bias and minimize errors in data entry (*DSMB approved change, 11.18.19*). Both the written record and the measure in REDCap will be verified. *Hard copy height and weight measurement forms will be uploaded to the secure REDCap database to allow the CCC, DCC and TFC to check for transcription and/or unit of measurement errors.* Any malfunctions of equipment will be reported to the study staff to resolve immediately. Any measurements outside of the range of normal will be flagged in REDCap and staff notified to retake measurements.

3. Masking Procedures

Masking refers to no knowledge regarding treatment assignment. It is not the same as concealment, which refers to random assignment to groups. Treatment masking represents an extension of concealment, to minimize bias in how participants assigned to different groups are treated. In the current study, the research assistants and coaches who are doing the measurements will be blinded, or masked as to treatment assignment, and the PIs for the Clinical Coordinating Center and Training and Fidelity Cores (Drs. [name] and [name]) and the DSMB will be masked as to treatment assignment. However, it is impossible to mask families, the family's PLAN coach, or pediatricians to group assignment. Families and PLAN coaches will

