- iii. "Please send me a confirmation email when you receive the instructions and consent form to your email."
 1. Follow-up with family 1 day after sending the email if you do not receive confirmation.
- iv. **REDCap consent procedure:**
 1. "You will receive an email from me in a few minutes. In it, there will be a link to the electronic consent form. Let me know when you have it open so I can go over it with you. [wait]"
 2. "This consent form is telling you about some updates to the study and is asking you to sign to agree to these changes."
 - a. Addendum: "First, as you know we will be doing your assessment remotely, meaning you will take heights and weights for all the PLAN participants in the study. Second, we will be paying your regular payment for the remote assessment. Third, we have changed the total payment for the 24 month assessment from \$50 to \$100. Last, we have started a lottery where you earn 1 chance to win an extra \$50 for every in person assessment you attend."
 - b. Reconsent: "I have sent a second email with another consent form for [child] to sign. Now that [child] has turned [age], they are old enough to sign a consent form for an older age group. This consent is just asking [child] to sign so we can keep doing the study just as we have in the past. There is nothing new in this consent form."
 3. "Please take your time and read over the form(s). If you have any questions, I can answer them. Whenever you are ready, you may scroll

to the bottom and “sign” your name with today’s date. (For reconsent: Please make sure your child is the one to sign and not you.) I will stay on the line with you until you are ready.”

e. Ask if they have:

i. “In order to complete the measurement you will need the following pieces of equipment. Please let me know if any of the following are not available to you:

1. PLAN Provided Weight Scale
 - a. Is their mailing address correct?
2. Carpenter’s Square
3. Metal Measuring Tape
4. Computer or phone access to internet and web camera
 - a. If they don’t have these, ask if they have some form of camera to take a picture of the measurements. Pictures can be emailed to the measurement coach.

ii. If these items are available:

a. “Great. Please have these items ready at the time of your measurement, we will provide you with a PLAN weight scale through the mail. Please confirm your mailing address and any special delivery instructions for your residence.”

iii. If an item(s) is not available:

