- b. PLAN Coach sends the family the link to 24-month video to describe PLAN website and handouts.
 - i. Sent during the assessment, but after the blinded assessor leaves the call
 - ii. Sent via email
 - iii. Include the PC's contact information

Thank the family for their participation.

Step 3: Measurement Coach Instructions for HEIGHT MEASUREMENTS

1. Confirm with family and/or coach that measurement is set for the scheduled date

2. Contact family at the day and time of assessment
 - a. If the family has a Webcam and Internet Access: use WebEx and/or Zoom
 - b. If they do not have a WebCam and Internet access: use phone to call the family and ensure they have a camera
3. Guide family through height and weight procedure, giving them feedback, answering any questions, making notes, and voicing corrections if they are needed
 - a. Assume the family has NOT read the instruction sheet and will need to be walked through the steps
 - b. Have them e-sign consent forms if they need to (see previous section)
 - c. Remind the family about which members need to be measured
 - d. Reference "Measurement Coach Checklist" with all the necessary information
4. Have family report their measurements aloud, and write them on a blank paper
5. Measurement coach will confirm accurate values and write them down on "Height and Weight form"
6. After the assessment, enter these values into REDCap as per normal protocol

Family Instructions for HEIGHT MEASUREMENTS

NOTE: Only children who enrolled in PLAN as participants need to have their heights measured. Parents or legal guardians enrolled in PLAN should measure the children's heights.

Location: On a level, non-carpeted, flat surface (e.g. wood, concrete floor, tile) against a door

Materials Needed:

[figure not shown]
1. Carpenter's square <https://www.homedepot.com/p/Empire-7-in-Polycast-Rafter-Square-296/100154430>
2. Metal measuring tape
3. Tape
4. Object of known height (ie participating parent, adult, yardstick)
5. Pencil or Pen
6. Piece of paper
7. Stool (especially if your child is taller than you)
8. Computer or phone with a web cam and internet access
 1. If you do not have a web cam and/or internet access, have a camera present

Procedure:

1. First, you will practice taking a height measurement with the carpenter's square and foldable yardstick.
 - a. Tape the foldable yardstick against a door with the bottom on a level, flat floor and it standing straight.

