NOTE: All participants who are enrolled in PLAN—parents and children—should measure their weight.

Location: On a level, non-carpeted, flat surface (e.g. wood, concrete floor)

Materials Needed:

1. PLAN weight scale

Procedure:

1. Before stepping on the scale, make sure:
 - a. You remove shoes, any items in your pockets, and any heavy pieces of clothing or jewelry, such as belts, hoodies, etc.
 - b. You use the restroom beforehand
2. Step on the scale
 - a. Stand straight, in the middle of the scale, with feet shoulder-width apart, looking straight ahead
 - b. Make sure your child does not move on the scale, as that can affect the accuracy of the measurement
3. Once the weight has stabilized, step off the scale and write down the weight.
4. Report the measurement to the measurement coach .
5. Repeat steps 2-5 to get a second weight
6. If measurements 1 and 2 differ by more than 0.25 pounds, your measurement coach will tell you to take two more weights.
7. Repeat steps 2-7 for every PLAN participant

Step 4: Wrapping up Assessment

1. PLAN Coach:
 - a. Thank the family and praise their efforts.
 - b. Identify families that will participate in the quality measurement of height to take a second measurement at a later date, confirm date and time. Follow protocol for remote height.
 - c. Instruct family to make confirm they received payment
 - d. Contact PC with payment amount and family address
 - e. Update site-specific tracking forms
2. Measurement Coach:
 - a. Enter data into REDCap
 - i. Check email to see if you received the pictures of the measurements
 - b. Contact PLAN Coach to notify that assessment was completed (or not completed)

Participant Instructions on Opening and Signing Consent Form

Steps:

1. Coach and participant will discuss how the consent form will be sent.
 - a. I.e. Email
 - i. Confirm email is correct and working
2. Coach will send the consent form to the participant and confirm that the participant has indeed received it.
3. Participant will open the email and download the document.
 - a. Once the form is downloaded, participant will open the form
 - b. The document will open up as a tab
 - c. This tab CANNOT be used to sign the form
 - i. Steps on how to sign the form will be below
4. Participant will close the tab and instead open the consent form manually from the 'Downloads' folder on the computer
5. To access the 'Downloads' folder:
 - a. Open up 'Start' menu option
 - b. Search for 'File Explorer'

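### At remote visits the unmasked family reads and reports weight and height, and no visible step requires the blinded assessor to see the scale display or the height mark

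*Combined protocol and SAP*

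**What the plan says.** All places are in the combined protocol and SAP.

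- **In-person weight** (Appendix C, Weight Procedures, steps 4-7): the coach stands beside the scale, watches the digital display settle, records the weight, repeats the reading, and only then has the participant step off.
- **Remote weight** (Family Instructions for Weight Measurements, steps 3-4): "Once the weight has stabilized, step off the scale and write down the weight". The family then reports the value to the measurement coach.
- **Remote height** (Family Instructions for Height Measurements, steps 12-15): an enrolled parent or guardian measures the child, marks the paper and reports the height.
- **Assessor's part** (Remote assessments Protocol, Step 3, items 2-6): the call is by video if the family has a webcam, otherwise by phone with a camera to be ensured. The blinded coach guides the family and is told: "Have family report their measurements aloud, and write them on a blank paper". Item 5 has the coach confirm that the values are accurate and write them on the form. Item 6 enters them in REDCap.
- **Photos**: for families without a webcam, "Pictures can be emailed to the measurement coach" (Step 1, item e). At data entry the coach is told: "Check email to see if you received the pictures of the measurements" (Step 4).
- **Other checks**: a repeat remote height in a random subset (Step 1, item 1), and an additional measurement at the pediatric office (Step 1, item i).
- **Masking**: Masking Procedures accepts that families cannot be masked. Masking of Assessment Staff relies on the standard Appendix C protocol to make measurement of the primary outcome objective.

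**The concern.** The primary outcome is computed from height and weight alone, and its protection against bias is that a blinded person measures both. At remote visits the order is reversed: the person who knows the arm reads the number, and the blinded person hears it. The visible text does not say how the coach is to confirm a weight once the participant has left the scale.

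The risk is differential reporting. Error common to both arms would largely cancel in the contrast. Error more frequent in FBT would not, and FBT families have a particular reason to care about the number: weight is part of their goal-setting and reinforcement system (Assessments), and their session frequency depends on weight change (Mastery-Based FBT Level System). Weight shaded down or height shaded up in FBT would favour FBT. As written, the procedure could not detect it, and no planned analysis would show whether the result depends on it.

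**Working it through.** **1. Who sees the value**

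| | In person | Remote |
|---|---|---|
| Reads the scale | coach | family |
| Timing of the record | before stepping off | after stepping off |
| Reads the height mark | coach | parent |
| Assessor's input | own sight of the reading | spoken report, then a confirmation whose method is not stated |

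**2. What the remote checks cover**

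- The repeat limits (0.3 cm, 0.25 lb) compare two family-reported values. Consistent shading passes.
- The quality-control repeat covers height only, in a subset, and follows the remote height protocol again.
- Photos are optional, and no step says what to do if none arrives.
- The office measurement has no precedence rule. Implementation of the Intention-to-Treat Principle ranks an available 24-month value above a pediatrician's clinic value. It does not say which counts as the 24-month value when a remote and an office follow-up value both exist.
- The five items under Sensitivity Analyses cover missing data, adherence, longitudinal models and covariates. None concerns measurement mode.

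**3. Scale of the outcome, as an illustration**

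No documented figure is disputed. To obtain a standard error, I reproduced one power entry first. Inputs: "Power computations for PLAN employ simulations and two-sided tests at the 0.05 level of significance"; "if we recruit 100% of our original target of 528 families"; "there is a 50/50 possibility of getting one treatment over the other treatment", so 264 per arm; 12 coaches, so 22 FBT families each; SD 15.3; ICC 0.04 (FBT) and 0.01 (UC).

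- SE = 15.3 × √[(1 + 21 × 0.04)/264 + (1 + 21 × 0.01)/264] = 15.3 × √(3.05/264) = 1.645.
- Power for a difference of 5.3, noncentral t with 11 df: 0.834. The plan's Table 1 gives 0.84.

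Remote share. The 24-month visit falls on or after 16 March 2020 for families randomized from 16 March 2018. That date is taken from the emergency COVID change under Adverse Event Assessment and Tracking.

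- Milestone table: 528 − 56 − 84 × 74/90 = 528 − 56 − 69.1 = 402.9, or 76%.
- Uniform accrual from 1 November 2017 to 15 August 2019: 517/652 days = 79%.
- Under either accrual pattern this is an upper bound, because it treats every later visit as remote. The documents give no resumption date.

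Effect on one child. Percent over BMI = 100 × (BMI/median − 1). I assume a 50 kg child at 50% over the median.

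- 0.5 kg under-reported: (0.5/50) × 150 = 1.5 points.
- Range: (0.5/60) × 130 = 1.1 to (0.5/40) × 170 = 2.1 points, for 40-60 kg and 30-70% over.
- 1 cm over-reported at 140 cm: 150 × [1 − (140/141)²] = 2.1 points.

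Effect on the contrast, for a net FBT-minus-UC under-report of 0.5 kg:

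| Share of 24-month values affected | Shift (points) | Two-sided rejection rate, no true effect |
|---|---|---|
| 50% | 0.50 × 1.5 = 0.75 | 0.07 |
| 76% | 0.76 × 1.5 = 1.14 | 0.10 |

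The last column uses SE 1.645 and 11 df. A shift of 1.14 is 22% of 5.3 (1.14/5.3). With no net difference in reporting, the shift is zero.

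**The case against.** The strongest reply is that verification was clearly intended. The coach is told to confirm the values before recording them. Video is the default and a camera is required otherwise. The coach walks the family through live and corrects them. Step 3 also refers to a Measurement Coach Checklist that is not reproduced and may say how to confirm. A practice height on an object of known size comes first, a subset of heights is repeated, and an office measurement is scheduled in addition. Nor does the 24-month reading drive later session frequency, since treatment ends there, and the remote payment does not depend on weight.

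Most of this stands, and it limits the claim. A reader might infer that the remote primary outcome is simply an unblinded self-report. The documents do not support that: confirmation is ordered, video may well have shown the display, and the office value may be the one analysed. What remains is that confirmation is undefined in the visible text, and the stated sequence takes the participant off the scale before the weight is reported.

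A reader might also set remote visits against the statement that "The handwritten weights will be manually entered into the REDCap database by a blinded measurement coach, which will eliminate potential measurement bias". That sentence carries an approval date of 18 November 2019, before the remote procedure, and concerns manual data entry. It is not a claim about remote visits.

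The second remote height goes on the sheet that carries the first mark. This is no special fault: in person, the same coach takes both heights knowing the first.

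**Conclusion.** The point holds as a gap in the remote procedure and in the analysis plan. The unmasked family reads and reports both components of the primary outcome, no visible step obliges the blinded assessor to see either, and nothing records or analyses whether the assessor did. The assurance under Masking of Assessment Staff is therefore not secured for remote visits.

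The size of any bias is unknown. The 1.1-point figure rests on three assumptions: a net 0.5 kg difference in reporting between arms, which no document supports or excludes; a 50 kg child at 50% over the median; and all visits due after mid-March 2020 being remote and open to shading, including those on live video. At 76% affected, the child-size range above gives 0.8 to 1.6 points (0.76 × 1.1 and 0.76 × 2.1). It would be wrong to infer that the FBT effect is biased by this amount, or that shading occurred. Sample size, power and the primary model are unaffected. This is a worthwhile, cheap improvement.

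**What to change.** 1. Reword the family weight steps 3-4 and Step 3, items 4-5. The participant stays on the scale with the display on camera, and the blinded coach reads and records the weight. The coach also reads the height mark against the measure on camera.
2. For families without video, request a photo of the display with the participant on the scale, and one of the marked sheet against the measure. If none arrives, still enter the value but flag it. Barring entry would turn a measured value into a missing one, to be imputed.
3. Add a REDCap field: in person, assessor-read remote, photo-verified, or family-reported only.
4. State in advance which value enters the primary analysis when remote and office values both exist. Add a sensitivity analysis that repeats the primary model without family-reported-only values.

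Cost: a minute or two more per call, one data field, one extra model run, and some values openly marked as unverified. For visits already completed, the flag can be set only where a recording, photo or coach note exists. The rest should be coded as family-reported only.
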